#### Resilience.

*Resilience:* The Connor-Davidson Resilience Scale (CD-RISC) is a self-report measure of resiliency comprised of 10 items rated on a five-point scale (0 = not true at all, 1 = rarely true, 2 = sometimes true, 3 = often true, 4 = true nearly all the time). Items capture various aspects of resilience including adaptability to change, availability and use of social support, and problem-solving style. Total scores range from 0-40; high scores indicate greater resilience. The CD-RISC has demonstrated good psychometric properties in previous research, including among medical populations.

*Measure of Current Status (MOCS-A):* The MOCS-A is a 13-item self-report measure of stress reactivity and coping, which will be administered at baseline and post treatment. It was developed to assess one's current self-perceived status on several skills targeted by the intervention, including the ability to relax at will, recognize stress-inducing situations, restructure maladaptive thoughts, be assertive about their needs, and choose appropriate coping responses. Statements are rated from 0 (I cannot do this at all) to 4 (I can do this extremely well). Scores range from 0-52; higher scores suggest better coping skills.

#### Secondary Outcomes: Psychosocial.

*Anxiety:* Anxiety symptoms will be assessed using the State form of the State-Trait Anxiety Inventory (STAI). The STAI State form is a 20-item self-report measure that has been used successfully to measure state anxiety in clinical and research settings. Respondents report the intensity of their current anxiety on a 4-point scale (1 = not at all, 2 = somewhat, 3 = moderately so, 4 = very much so). Scores range from 20-80, with higher scores indicating greater anxiety. This measure has been widely researched and used, and previous studies have found that the STAI is consistently reliable and valid.

*Depression:* Depressive symptoms will be assessed using the Center for Epidemiologic Studies – Depression scale (CES-D). This is a 20-item self-report measure that screens for depression and depressive episodes. Respondents report how often they experienced symptoms associated with depression on a 4-point scale (0 = rarely or none of the time, 1 = some or a little of the time, 2 = occasionally or a moderate amount of the time, 3 = most or all of the time). Scores range from 0 to 60; high scores reflect greater depressive symptoms. The CES-D has been found reliable (Alpha >.85) in previous research among medical populations, women in midlife, and older adults. It has also been found to have good sensitivity and specificity.

*Social support:* Social support will be assessed using the Medical Outcomes Study Social Support Survey. The Medical Outcomes Study Social Support Survey is a 20-item self-report measure of emotional/informational support, tangible support, and positive social interaction. Respondents rate on a 5-point scale (1 = none of the time, 2 = a little of the time, 3 = some of the time, 4 = most of the time, 5 = all of the time) how often each type of social support is

available to them if they need it. The measure has good reliability and was found to be fairly stable over a one-year period.

*Quality of life:* Health related quality of life will be assessed using the AIDS Clinical Trials Group quality of life assessment, the Multidimensional Health Status Assessment. This is a self-report measure, in which individuals report the effect of their health on their quality of their existence across multiple domains including physical and psychological functioning. Items on this scale also assess the extent to which pain and fatigue have a negative impact on quality of life. Previous research has consistently confirmed that the assessment is highly reliable and valid, and it is used extensively in HIV research.

*HIV stigma:* HIV stigma will be assessed using the HIV Stigma Scale, a widely used measure of personalized stigma, disclosure concerns, negative self-image, and concern with public attitudes toward people with HIV. Respondents report their experiences of stigma on a 4-point scale (strongly disagree to strongly agree), with a total score ranging from 0 to 75. The measure has been validated among adults living with HIV (alpha = 0.88).

*Substance use:* The Addiction Severity Index-Lite (ASI-Lite) will be used to assess lifetime and recent substance use, including severity. It also asks about route of administration and if any substance use is prescribed. The number of items depends on substances endorsed. It has good internal consistency (alpha = 0.61 – 0.89).

*Coping:* Coping strategies will be assessed using the Brief COPE. This is a 28-item measure rated on a 4-point scale (I haven't been doing this at all to I've been doing this a lot) evaluating how often individuals engage in specific strategies in response to specific stressors. It consists of 14 subscales (self-distraction, active coping, denial, substance use, use of emotional support, use of instrumental support, venting, behavioral disengagement, positive reframing, planning, humor, acceptance, religion, self-blame). Total scores range from 28 to 112, with higher scores indicating greater use of the coping strategy.

*Sexual functioning:* Sexual functioning will be assessed using the Female Sexual Function Index, a 19-item gender-specific measure that asks about sexual functioning across six domains (desire, arousal, lubrication, orgasm, satisfaction, pain). Total scores range from 2 to 36, with higher scores representing higher sexual functioning. The measure was developed for women with female sexual arousal disorder but has also been validated in the general population. It has good internal consistency (alpha = 0.78 – 0.84).

*Sexual communication:* Sexual communication will be assessed using the 6-item version of the Dyadic Sexual Communication (DSC) Scale, a measure of how individuals perceive discussions surrounding sexual matters with their partners. Items are rated on a 6-point Likert scale from 1 (disagree strongly) to 6 (agree strongly), with total scores ranging from 13 to 78, and higher scores indicating higher quality of communication. The original measure has been found to have good internal consistency (alpha = 0.81).

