## **1. SPECIFIC AIMS**

**Specific Aims.** This is the second phase of a two-part study. In the first phase (MGH IRB Protocol #2017P000404), we adapted an existing resiliency intervention, the Relaxation Response Resiliency Program (3RP), to the needs of women ages 50 and over who are living with HIV. We conducted preliminary testing of the refined group intervention via an open pilot study (N=13 enrolled) across two sites, MGH and Boston Medical Center), and conducted individual exit interviews to solicit feedback on the intervention, including experiences with the assessment protocol, intervention content, and number and duration of sessions. Data from these interviews were used to make adaptations to the manual in an iterative fashion after each of the three open pilot groups, and the final product will now be tested via a small randomized controlled trial.

Specifically, we will conduct a randomized study (N=up to 60) of the adapted 3RP intervention among groups of women living with HIV, ages 50 and over. Our primary aim is to test the feasibility and acceptability of all study procedures; we hypothesize that our protocol will be both feasible and acceptable. We will also examine data on the effect of the intervention on primary (e.g., resilience) and secondary outcomes of interest, but these analyses are purely exploratory, and we are most interested in how well our selected measures may be sensitive to change. Secondary outcomes will include changes in measures of psychosocial distress (depressive symptoms, anxiety, social support, and quality of life) and HIV / physical health outcomes (suppressed viral load, decreased symptom burden, improved cognitive and physical status). We hypothesize that participants in the treatment condition will experience greater improvements in resilience, psychosocial distress, and HIV / physical health outcomes. Data from this second phase of the study will inform the eventual development of a full-scale randomized controlled trial.

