integrating positive psychology strategies (an outline of the 3RP intervention is provided) interwoven among traditional relaxation-based behavioral strategies and cognitive-behavioral skills. For example, Cognitive Behavioral Stress Management (CBSM) protocols make use of tools such as cognitive restructuring, guided imagery, breathing exercises, and communication skills, some of which are also contained in the 3RP. However, cognitive restructuring in the 3RP is focused not only on modifying maladaptive cognitions, but on eliciting a positive emotion to guide a more adaptive response and thus drawing meaning from stressful events. While CBSM focuses on enhancing social relationships, this is achieved primarily through improving communication skills. The social focus of the 3RP intervention involves an assessment of available types of social support, and in the proposed modifications, problem-solving ways to close perceived gaps in support to enhance one’s sense of connectedness to themselves and others. The 3RP intervention also focuses extensively on mindful awareness skills to improve the experience of daily living.

**Few interventions have been developed for older adults with HIV; none focus on women, nor do existing interventions use a “strengths based” approach.** A recent review of interventions for older adults with HIV concluded that, overall, there is a dearth of interventions available for this population. Of the six interventions reviewed, the study populations were all predominantly male, and none attempted to develop strengths that may affect the full spectrum of factors that influence healthy aging with a chronic illness. The authors conclude that subsequent interventions must be more “representative... of the older adult population living with HIV”. Thus, the scientific community is compelled to develop interventions that may meet the specific needs of older women living with HIV.

Figure 1: Conceptual model

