Throughout the program, participants will set goals for their weekly relaxation practice, in addition to other self-determined goals related but not limited to healthy lifestyle behaviors, HIV management, social support, and valued action. Progress on goals will be evaluated and new goals will be set over time. For example, if an individual articulates that she values service to the HIV community, but is not currently engaged with that community, goals may include researching options for involvement, contacting agencies of interest, and eventually applying to serve as a volunteer.

As described above, some of the most common challenges for older women living with HIV are anxiety, depression, loneliness, managing multiple medical comorbidities, chronic pain, fatigue, sexuality, and stigma. In Table 3, we highlight how the skills contained in our modified 3RP intervention target these issues.

Table 3: Skills Table

Common concerns for older women living with HIV	Current intervention skills	Additional skills added to existing intervention
Stress of managing a chronic long-term, life threatening illness; toxicities associated with long term use of ARVs; additional medical comorbidities	Eliciting the relaxation response (e.g., meditation, chair yoga; imagery); optimizing recuperative sleep; cognitive reappraisal; building a positive perspective; acceptance based coping skills; physical activity and nutrition recommendations	Supporting healthy lifestyle behaviors (e.g., how to manage health in the context of HIV); self-compassion
Pain and fatigue	Eliciting the relaxation response (e.g., meditation, chair yoga; imagery); cognitive reappraisal	Supporting healthy lifestyle behaviors (e.g., pacing); self-compassion
Stigma and social isolation	Evaluation of current social support; cognitive reappraisal; building a positive perspective; acceptance based coping skills	Valued action; problem-solving around developing healthy social supports; self-compassion
Depression and anxiety	Eliciting the relaxation response (e.g., meditation, chair yoga; imagery); cognitive reappraisal; building a positive perspective; acceptance based coping skills; physical activity and nutrition recommendations	Valued action; problem-solving around developing healthy social supports; self-compassion
Sexuality concerns	Cognitive reappraisal	Education around HIV prevention; development of sexuality goals; problem-solving barriers to goals; self-compassion

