## STATISTICAL ANALYSIS PLAN

## Statistical Plan for Analyses

Power: PAR-14-182 states, "...the R34 should ... enhance the probability of reaching more definitive outcomes in a larger trial... by working out the details of the experimental protocols, including the assessment protocol, the...intervention protocol, as well as the comparison intervention protocol and randomization procedures; examining the feasibility of recruiting and retaining participants into the study conditions; ... collection of preliminary data regarding feasibility, acceptability, safety, tolerability, and target outcomes is appropriate. Given the limited sample sizes that can be supported under this...mechanism, proposing the use of a comparison group for conducting fully powered tests of outcomes (i.e., efficacy) or attempting to utilize the highly variable point estimate of an effect size for power calculations would not be appropriate." As stated in the specific aims, we aim to test the feasibility and acceptability of all study procedures as a primary goal; we will not attempt to use our data to estimate an effect size. We are interested in the sensitivity of our selected measures to detect change. Thus, as an exploratory outcome, we propose to examine the intervention effect of resilience and other secondary outcomes. We have conducted power calculations to ensure any lack of effect would be unrelated to power. We also explored current funded R34 studies of similar scope that are currently funded by NCCIH, and our sample size is well within the range of what is documented in these studies (e.g., 5R34AT008423, 1R34AT007935).

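### The only Brief COPE score the protocol defines is an all-item total with no direction of benefit, which may partly mask a change in coping

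*Combined protocol and SAP*

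**What the plan says.** The protocol describes the instrument under Secondary Outcomes: Psychosocial (Coping): "This is a 28-item measure rated on a 4-point scale". It then lists the subscales: "It consists of 14 subscales (self-distraction, active coping, denial, substance use" and ten more, among them planning, acceptance, humor, religion and self-blame. The only score it defines follows: "Total scores range from 28 to 112, with higher scores indicating greater use of the coping strategy". It gives no subscale range, composite, reverse-keying or direction of benefit.

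The analysis text, in the protocol's Data analytic plan and again in the SAP under Analyses, compares every outcome between arms with a mixed model. It does not say which Brief COPE score enters that model. The SAP's power section covers resilience, depressive symptoms and quality of life, not coping.

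Specific Aims says that the main interest in the outcome data is "how well our selected measures may be sensitive to change". The SAP repeats it: "We are interested in the sensitivity of our selected measures to detect change".

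**The concern.** A total over all 14 subscales mixes strategies that the program teaches with strategies that few would count as improvement. Table 3 lists among the intervention's skills "cognitive reappraisal; building a positive perspective; acceptance based coping skills", and Tables 2 and 3 add problem-solving, social support and humor. On the other side of the same sum stand denial, substance use, behavioral disengagement and self-blame. A participant who plans more and denies less may show little movement. One who drinks more to cope moves the total in the same direction as one who seeks more support.

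The other main scales, such as the CD-RISC, MOCS-A, STAI and CES-D, each come with a direction that has a better-or-worse meaning. This one does not. The exploratory analyses are meant to show whether the chosen measures respond to change and to inform a full-scale trial. A total that responds poorly because of its construction could be mistaken for a coping instrument that responds poorly.

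**Working it through.** **1. What the stated range is.** Inputs from the protocol: 28 items, 4 response points, 14 subscales.
- Coded 1 to 4: 28 × 1 = 28 and 28 × 4 = 112, which reproduces the stated range. Coded 0 to 3, it would be 0 to 84.
- 28 / 14 = 2 items per subscale, so a subscale would run from 2 to 8.
- The stated score is therefore the sum over all 14 subscales. The range alone cannot exclude reversed items, since a reversed item also runs from 1 to 4. The stated direction, greater use, implies that none is reversed.

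**2. Check of the power method against the plan's own figures.** The SAP uses 30 per arm and a two-sided 0.05 level. With noncentral t, 80% power needs d = 0.736. At the SAP's SD of 11.8 that is 0.736 × 11.8 = 8.68 points (stated 8.7). The paired version gives 6.24 (stated 6.2). The method agrees with the plan.

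**3. Illustration of the offset.** The documents give none of the inputs below, so all are assumptions:
- the 14 subscale changes have equal variance and common correlation ρ, from 0 to 0.3;
- 8 helpful subscales rise by 0.5 SD relative to control, 4 unhelpful ones fall by 0.5f SD, and 2 do not move.

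Formulas:
- total: d = 0.5(8 − 4f) / √(14 + 182ρ), where 182 = 14 × 13;
- composite of the 8 helpful subscales: d = 4 / √(8 + 56ρ), where 56 = 8 × 7.

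Denominators: for the total, √14 = 3.74 at ρ = 0 and √68.6 = 8.28 at ρ = 0.3. For the composite, √8 = 2.83 and √24.8 = 4.98.

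| Score | Raw gain kept | d, ρ = 0 | Power | d, ρ = 0.3 | Power |
|---|---|---|---|---|---|
| Composite of 8 helpful | – | 4/2.83 = 1.41 | above 99% | 4/4.98 = 0.80 | 86% |
| Total, unhelpful fall equally (f = 1) | 50% | 2/3.74 = 0.53 | 53% | 2/8.28 = 0.24 | 15% |
| Total, unhelpful fall half as much (f = 0.5) | 75% | 3/3.74 = 0.80 | 86% | 3/8.28 = 0.36 | 28% |
| Total, unhelpful unchanged (f = 0) | 100% | 4/3.74 = 1.07 | 98% | 4/8.28 = 0.48 | 45% |

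In the last row nothing offsets. The loss comes only from adding subscales that do not move.

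**4. The extreme case.** With 7 subscales up and 7 down by the same amount, the net change is 0.5 × (7 − 7) = 0, and the rejection rate is the 5% type I error. This needs exact balance.

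**5. Limit of the illustration.** A common positive ρ also assumes that helpful and unhelpful changes correlate positively. If they correlate negatively, the total has a smaller variance and loses less than the ρ = 0.3 columns show. The direction of the effect is firmer than its size.

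**The case against.** The strongest reply is that the Coping paragraph describes an instrument and does not commit to an analysis. It names all 14 subscales, and its reference to a single coping strategy fits a two-item subscale better than a total. This stands in part: the documents never say outright that the total will be the analysed outcome. But they define no other score. If subscales were intended, nothing says which ones or in what direction, and the planned multiplicity adjustment needs a defined family.

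Second, a reader might infer that the intended changes cancel, so that the measure is bound to look insensitive. The documents do not support that. They support raising acceptance, reappraisal, support, problem-solving and humor. They name neither denial, substance use nor behavioral disengagement as something to lower. The nearest text concerns thoughts: "cognitive restructuring in the 3RP is focused not only on modifying maladaptive cognitions, but on eliciting a positive emotion to guide a more adaptive response". Active, untreated and interfering substance abuse is also an exclusion, which may limit how far substance-use coping can fall. Offset is therefore possible, probably partial, and of unknown size.

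Third, the documents label no subscale adaptive or avoidant. That is correct, and any split is a judgement for the sponsor. Venting, self-distraction and religion in particular are not settled by the text.

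Fourth, the outcome analyses are exploratory, item responses are collected so other scores can be computed later, and the MOCS-A measures coping skills with a clear direction. This limits the weight of the point. It does not remove it. Scores chosen after the data are seen are weaker evidence of sensitivity to change, and the MOCS-A measures self-perceived skill rather than strategies used. Its own description also schedules it only at baseline and post-treatment, although the study procedures read more broadly.

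**Conclusion.** The point holds in a limited form. The one Brief COPE score that the protocol defines is an unreversed sum over all 14 subscales. A higher value has no better-or-worse meaning, and it is a poor instrument for the study's stated question about sensitivity to change. That much follows from the text and from 28 × 1 and 28 × 4.

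How much change would be masked is not known. Under the assumed eight-up, four-down pattern, power for the total runs from 86% down to 15%, depending on the correlation and on how far the unhelpful subscales fall. The helpful composite has above 99% to 86%. Complete cancellation is a special case that needs exactly balanced changes. All these figures rest on assumed effects, equal variances and a common correlation, because the documents give no Brief COPE values.

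Feasibility and acceptability, the primary aim, are not touched. The plan should be changed before analysis because the change is cheap and the scores bear on which measures go forward.

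**What to change.** Do not use the all-item total as the analysed coping outcome. Before analysis, amend the Coping paragraph and the SAP's Analyses section to:

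- name the scores to be analysed, built from items already collected. One possibility is a composite of strategies that the program teaches (such as active coping, planning, positive reframing, acceptance, humor and support) and a second of denial, substance use, behavioral disengagement and self-blame. The sponsor should choose and justify the membership, including where the remaining subscales go;
- state each score's item coding, range and direction of benefit;
- include these scores in the family covered by the planned multiplicity adjustment;
- report the 14 two-item subscales descriptively.

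Cost: a wording change and, with two composites in place of one total, one more score in the multiplicity family. No new data or extra participant burden.

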#### Secondary Outcomes: HIV/Physical Health.

The proposed content on how to manage health in the context of HIV (See Table 3) provides information on the importance of sustained adherence to antiretroviral therapy and continued engagement in HIV care, as one must adequately manage their disease to be truly resilient in the face of HIV infection. Individuals will generate plans and back-up plans on how to manage common barriers to antiretroviral adherence, as well as engagement in HIV care. Thus, we will assess variables related to HIV management, to measure the performance of this content. Data

on time since HIV diagnosis will be assessed at baseline. The following variables will be assessed: current antiretroviral therapy regimen, adherence to antiretroviral therapy regimen, and engagement in HIV care.

*Engagement in HIV care:* On average, persons living with HIV should meet with their HIV provider four times per year. We will ask participants when they last saw an HIV care provider.

*Adherence to antiretroviral therapy:* Adherence will be assessed via self-report. Data on self-reported adherence will be collected each week using the participant “weekly adherence to skills” forms described below. The questions will be based on standardized questions for self-report assessment of adherence to antiretroviral therapy. A list of common antiretroviral medications will be provided along with the adherence assessment in order to facilitate participant memory and enhance self-report.

*CD4 and viral load:* CD4 count will be assessed at baseline only, while viral load will be assessed at baseline, post-treatment, and 3-month follow-up visits. At the baseline assessment, patients will have two tubes drawn by a phlebotomist at the MGH Clinical Research Center (CRC), located in the White Building 12 at [name]. One EDTA (lavender top) tube will be used for HIV viral load measurements (10 ml of blood) and another for CD4 (3 ml of blood). Per hospital clinic protocol, each visit will include an intake and measure of vital signs prior to the blood draw. At subsequent major assessment visits (post-treatment and three-month follow-up), only one tube will be drawn. All blood samples will be analyzed at the MGH Core Lab, located in the Warren Building 225 at [name], and results will be available within 5-7 business days for the viral load, and 24-48 hours for the CD4 count. Recent viral load and CD4 count will be abstracted from participants' health records if they are patients at MGH. The purpose of this is to save participants an unnecessary blood draw if they have recently had these tests done during a clinical visit. Both MGH patient registration status and recent clinical blood draw history will be determined during screening process. All blood draws are optional; participants may opt out if they so choose.

*Symptom burden:* Symptom burden will be assessed using the using the AIDS Clinical Trials Group Symptoms Distress Module, an instrument that measures distress related to HIV symptoms, and asks participants to rate on a 5-point scale (0 = I do not have this symptom, 1 = it doesn't bother me, 2 = it bothers me a little, 3 = it bothers me, 4 = it bothers me a lot) how much each of 20 symptoms (e.g., fatigue, nausea, muscle aches) bothered them during the past four weeks. The instrument is reliable and valid, is used extensively in HIV research and has also demonstrated cross-cultural validity.

*Cognitive status:* Cognitive status will be assessed using the Mini-Cog. The Mini-Cog can quickly detect cognitive impairment through its three-item recall test and a clock-drawing test (CDT) administered by a clinician. Respondents score as positive for cognitive impairment if they recall no words, or recall 1 or 2 words with an abnormal CDT. Both measures have been used with older adults in various health care settings, and previous research has found consistently good reliability and validity.

*Weekly adherence to skills:* Practice notes have been developed to correspond with each module of the 3RP treatment. Participants will be asked to keep brief daily diaries of their out of session practice (e.g., completion of 15 minutes of meditation, engaged in activities to foster social connectedness, engaged in a desired lifestyle behavior, etc.). These diaries will be used to generate a rating of adherence to out of session practice guidelines. If group sessions are conducted virtually via Zoom, participants in the intervention group will be mailed an envelope

containing weekly practice notes to be completed during the 10-week group program. Participants will then be asked to mail back the completed practice notes (via a pre-paid envelope) at the end of the program.

*Treatment Credibility and Expectancy:* The Treatment Credibility/Expectancy Questionnaire (CEQ) is a widely used 6-item measure that assesses treatment credibility and expectancy. Participants are asked to rate the treatment from 1 (not at all) to 9 (very much) and from 0% (not at all) to 100% (very much). The percentage ratings are subjected to linear transformation with a minimum of 1 and a maximum of 9. We will administer the scale after the first treatment session.

*COVID-19-related:* Quantitative assessments and the qualitative exit interview will contain COVID-19-related items in order to better understand the impact of COVID-19 and corresponding public health restrictions on participants' lives (e.g., mental health, ability to adhere to HIV medications), and their experience participating in this study.

